**2. Seizure frequency**

Seizure frequency from the subject’s diary data will be evaluated by standardizing the sum of seizures to a frequency per 4 weeks (28 days). The standardized seizure frequency (SSF) for any given period (including baseline) will be calculated as:

$$\frac{\text{Total number of seizures reported in the diary during the interval of interest}}{\text{Number of days on study for the interval of interest}} \times 28 \text{ days}$$

The number of days on study for the interval of interest will be determined by:

$$\text{Visit Date of last visit during the interval of interest} - \text{Visit Date of first visit during the interval of interest}$$

**3. Relative change in seizure frequency from baseline**

Seizure frequency change from the baseline period will be evaluated by using SSF per 4 weeks (28 days). The baseline period is the period from Visit 1 to Visit 2 from Protocols 093-045 or 093-046.

The relative (%) change in SSF for any interval of interest (including baseline) will be calculated as:

$$\frac{(\text{SSF during the interval of interest}) - (\text{SSF during baseline period})}{\text{SSF during baseline period}} \times 100$$

Further the relative change from baseline will be categorized into:

- 100% Decrease
- ≥ 75% - < 100% Decrease
- ≥ 50% - < 75% Decrease
- 0% to < 50% Decrease
- > 0% to < 25% Increase
- ≥25% to <50% increase
- ≥50% to <100% increase
- ≥100 % increase

**4. Responder rate**

Responder is defined as having a ≥50% reduction in SSF from baseline.

The proportion will be calculated as the number of responders divided by the total number of subjects in the ITT population entering the period of interest.

**5. Seizure-free**

Subjects who did not have any seizure as per the seizure diary during that time period will be deemed seizure free, for the corresponding interval of interest. However, subjects who discontinue prior to Visit 7 will be considered not seizure-free for the interval when the discontinuation takes place and all subsequent intervals (even if the subjects are seizure-free at the time of discontinuation). That is, subjects must complete each interval of interest without any seizures to be considered seizure-free for each interval of interest.

The number and percent of seizure-free subjects will be presented for the interval of interest, for each interval the percent will be based out of the number of subjects in the ITT population entering each interval of interest.

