### **6.2 Handling of Dropouts or Missing Data**

Subjects who dropped out before study completion are not to be replaced and all available information obtained from them will be included in the appropriate efficacy

and safety summaries to the time of dropout. No imputation is planned for any safety measures.

If the date of the seizure is missing or incomplete and the seizure cannot be allocated to a study interval, these data will not be used in the analysis, but will be presented in the subject data listings. If the seizure diary was returned and there was no seizure data available for a particular day during that evaluation period, it will be assumed that the patient had missing seizure data, and the day will be excluded from the calculation of the standardized seizure frequency.

Seizure related variables will be calculated based on available data. For dropout subjects, their seizure frequency will be derived for each interval up to the last interval where the subject had data. The last interval standardized seizure frequency will be computed based on available data prior to dropout.

For QOLIE31 and MADRS, if only one item is missing, it will be imputed by the average of other items for calculating the total score (See Section 5.2.4: 1 and 2).

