**Seizure-free**

The number and proportion (%) of subjects that are seizure-free with 95% confidence intervals (using binomial methods) will be presented for 1 week, 1 month, each 3-month visit window and overall.

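### The seizure-free rule sets no minimum diary coverage, so unobserved days count as seizure-free for subjects who stay in the study

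*SAP*

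**What the plan says.** SAP 5.2.2 item 5 gives the main rule: "Subjects who did not have any seizure as per the seizure diary during that time period will be deemed seizure free". One override follows: "subjects who discontinue prior to Visit 7 will be considered not seizure-free for the interval when the discontinuation takes place", and for all later intervals. The item then sums up: "subjects must complete each interval of interest without any seizures to be considered seizure-free for each interval of interest". On the denominator it says: "for each interval the percent will be based out of the number of subjects in the ITT population entering each interval of interest".

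SAP 6.2 deals with gaps. If a diary came back but a given day has no seizure data, "it will be assumed that the patient had missing seizure data, and the day will be excluded from the calculation of the standardized seizure frequency". The same section adds a general rule: "Seizure related variables will be calculated based on available data". It says nothing about a diary that was not returned.

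SAP 7.6 reports the number and proportion seizure-free, with binomial 95% confidence intervals, at 1 week, 1 month, each three-month window and overall. It names no minimum coverage, no not-evaluable class and no sensitivity analysis for this endpoint.

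SAP 5.2.1 has subjects or caregivers record seizures in the diary, which is reviewed and collected at Visits 2 through 7. It describes no daily entry confirming that no seizure occurred.

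**The concern.** The SAP treats the same gap in two ways. For SSF, a day without data is unknown and leaves the calculation. For seizure freedom, that day raises no obstacle and in effect counts as a day without seizures.

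The rule is also uneven between subjects. Take a 91-day window. A subject who stays in the study with 28 observed days and no recorded seizure is seizure-free for the whole window. A subject who leaves after 90 fully observed days without a seizure is not. Incomplete observation is penalised when it comes from discontinuation and ignored when it comes from an incomplete diary.

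Maintenance of therapeutic effect is a secondary objective (SAP 2.2), and seizure freedom is one of the endpoints that describe it. If the true proportion is low, a few poorly observed subjects could make up a visible part of the reported figure, and the planned tables would not show it.

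**Working it through.** **No figure to reproduce.** The documents state no expected seizure-free rate and no amount of missing diary data, and SAP 3.3 places the sample size outside statistical considerations. What follows is an illustration on assumed inputs.

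**Does any sentence already require coverage?** The sentence about completing each interval is introduced as a restatement of the discontinuation rule, so it concerns staying in the study, not filling in the diary. The available-data rule in 6.2 sets no minimum. Read literally, a retained subject with no usable diary days qualifies.

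**Assumptions.** Seizures are Poisson at L per 28 days. A three-month window is 91 days. A share c of days is observed, with gaps unrelated to seizures.

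**One retained subject.** P(no recorded seizure) = exp(−L × c × 91/28).

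| Coverage c | L = 1 | L = 2 |
|---|---|---|
| 100% | 3.9% | 0.15% |
| 50% | 19.7% | 3.9% |
| 25% | 44.4% | 19.7% |
| 10% | 72.3% | 52.2% |
| 0% | 100% | 100% |

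The 100% row is the true probability. Every other row is higher, so the error among retained subjects cannot be downward.

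**Reported proportion, no discontinuation.** Let a share m of subjects have coverage c and the rest full coverage. Rate under the SAP rule = (1 − m) × exp(−3.25L) + m × exp(−3.25Lc).

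- L = 1, m = 10%, c = 25%: 0.9 × 0.0388 + 0.1 × 0.4437 = 7.9%, against a true 3.9%; about 4 points too high.
- Counting the low-coverage subjects as not seizure-free: 0.9 × 0.0388 = 3.5%, slightly below the truth.
- Over L = 0.5 to 2, m = 5% to 20% and c = 10% to 50%, the excess runs from 0.2 to 13.7 points.

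**Adding the discontinuation rule.** Suppose 10% of those entering discontinue and have the same seizure rate. The SAP rate is then multiplied by 0.9.

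- L = 1, m = 10%, c = 25%: 0.9 × 7.93% = 7.1%, against a true 3.9%. Net error upward.
- L = 0.5, m = 5%, c = 50%: 0.9 × 20.93% = 18.8%, against a true 19.7%. Net error downward.

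**Interval length, at c = 50%.**

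- L = 1: the excess is 19.7% − 3.9% = 15.8 points over 91 days. Over 364 days it is exp(−6.5) − exp(−13), about 0.15 points.
- L = 0.1: the excess is 85.0% − 72.3% = 12.8 points (before rounding) over 91 days, and 52.2% − 27.3% = 25.0 points (before rounding) over 364 days.

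Which interval suffers more depends on the seizure rate.

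**The case against.** The strongest objection concerns the remedy. SAP 5.2.1 describes a log of seizures. If the diary holds no daily confirmation, a truly seizure-free subject has no seizure data on any day, and 6.2 read literally would give that subject zero coverage. A threshold added without first defining an observed day could then fail exactly the subjects who are seizure-free. This stands, and it sets the order of the fix. The diary form is not in the documents supplied; the amendment summary says only that it was replaced and later simplified. Nothing in the documents supports a particular cut-off such as 90%.

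The SAP can also be defended as having chosen an available-data rule, backed by diary review at each visit and by diary listings (SAP 7.6). Review may keep gaps small, but it sets no minimum, and listings do not alter the reported proportion.

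Finally, this is a descriptive secondary endpoint in an open-label extension whose primary objective is safety. That limits the priority of the point without removing it.

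**Conclusion.** The point holds in limited form. As written, the rule can count unobserved time as seizure-free for subjects who stay in the study, and among them the error is upward or zero. That direction needs no model. The sizes shown rest on assumed seizure rates, coverage, shares of poorly covered subjects and gaps unrelated to seizures; the actual size is unknown.

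Two stronger readings are tempting, and the documents support neither.

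- A reader might infer that the reported seizure-free rate is overstated. Counting discontinuers as not seizure-free pulls the other way, and the net error can take either sign, so net bias is not established.
- A reader might infer that the overall 1-Year figure is affected most because it spans the most days. At 1 seizure per 28 days and half coverage the reverse is true; only at much lower rates does the longer interval suffer more.

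The plan should be changed, at moderate priority: the correction is analytic and cheap, and without it a reader cannot tell whether the rate depends on missing diaries.

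**What to change.** 1. In SAP 6.2, define an observed diary day so that a day confirmed as seizure-free counts as observed. One workable form is a day covered by a returned and reviewed diary and not flagged as missing. State that an unreturned diary is missing for the days it should have covered.
2. In SAP 5.2.2 item 5, require all three of: no recorded seizure, completion of the interval, and a pre-specified minimum share of observed days. The sponsor chooses the value before database lock. Subjects below it count as not seizure-free, as discontinuers already do.
3. In the SAP 7.6 seizure-free table, report for each interval how many subjects fail on coverage alone, and show the current definition alongside as a sensitivity row.

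The cost is a few SAP sentences and one derived coverage variable, with no new data collection if diary return and missing-day flags are already captured. The reported rate may fall, and it can fall slightly below the truth because some poorly observed subjects will really have been seizure-free. The two rows together let the reader see how far the result depends on coverage.

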**Relative (%) change from baseline in SSF**

Relative (%) change from baseline in SSF will be summarized descriptively for 1 week, 1 month, each 3-month visit window, overall, and by the following subgroups: number of baseline AEDs, and baseline AED medications, seizure type. The number and percentage of subjects with the category in Section 5.2.2 will also be presented.

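### In the seizure-free rule, the words carrying a dropout forward as a failure to later intervals change no 3-month percentage, so in windows 2 to 4 this rate and the responder rate can rise through selective dropout alone (minor)

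*SAP*

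**What the plan says.** Four parts of the SAP bear on this.

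- **Seizure-free (5.2.2 item 5).** The dropout rule is that "subjects who discontinue prior to Visit 7 will be considered not seizure-free for the interval when the discontinuation takes place and all subsequent intervals", and it applies "even if the subjects are seizure-free at the time of discontinuation". The denominator follows in the next paragraph: "for each interval the percent will be based out of the number of subjects in the ITT population entering each interval of interest".
- **Responder rate (5.2.2 item 4).** A responder has at least a 50% reduction in standardized seizure frequency (SSF). The rate is the "number of responders divided by the total number of subjects in the ITT population entering the period of interest". Item 4 sets no completion condition.
- **Dropouts and SSF (6.2).** "For dropout subjects, their seizure frequency will be derived for each interval up to the last interval where the subject had data". For the interval of dropout itself, "The last interval standardized seizure frequency will be computed based on available data prior to dropout".
- **Reporting (6.1 and 7.6).** The first year has four 3-month windows, each opening at or after a visit and closing before a later one. Seizure-free and responder rates are given with 95% binomial confidence intervals for 1 week, 1 month, each window and overall.

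Maintenance of therapeutic effect is a secondary objective (2.2). The SAP does not define what it means to enter an interval. The protocol file available here is a summary of amendments, so whether the full protocol defines it cannot be checked.

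**The concern.** The seizure-free rule appears designed to stop dropout from flattering the results: once a subject leaves, that subject is a failure from then on. The denominator undoes the second half of that. Someone who left in window 1 is not among those entering windows 2, 3 or 4. Calling that subject a failure there adds nothing to the denominator and removes nothing from the numerator.

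The responder rate has the same denominator and so the same exposure. A reader judging maintenance of effect will look at these rates window by window. If subjects who do badly are more likely to leave, the series rises even though no individual has improved, and the confidence intervals move up with it.

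**Working it through.** The plan states no dropout rate, response rate or power for these endpoints, so there is no planned figure to reproduce. All rates below are assumptions.

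**1. What each half of the seizure-free rule does.** Take 348 subjects (the planned number in the Amendment 3 summary, used only for scale), 10% dropout per window, 20% seizure-free among those completing a window, and 20% of leavers seizure-free up to leaving. In window 2, 313 enter, 31 leave and 282 complete. Of these, 56 completers and 6 leavers have had no seizure.

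- Rule as written: 56/313 = 17.9%.
- Carry-forward words deleted: still 56/313 = 17.9%. The 35 who left in window 1 are in neither count, so the change is 0.0 points.
- Whole dropout rule deleted: (56 + 6)/313 = 19.8%.

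The same-interval half therefore works. Its effect is roughly the share dropping out times the share of leavers seizure-free to date. That runs from 5% × 10% = 0.5 points to 15% × 40% = 6.0 points.

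**2. Selective dropout and the responder rate.** Let 100 enter and 40 respond. The same number leave in each of windows 1 to 3, and none in window 4. Planned rate = responders among those entering ÷ number entering. A leaver who was responding counts as a responder in the window of leaving, under Section 6.2.

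| Leavers per window | Responders among leavers | Window 1 | Window 2 | Window 3 | Window 4 | All-ITT, window 4, dropouts as failures |
|---|---|---|---|---|---|---|
| 10 | 0% | 40/100 = 40.0% | 40/90 = 44.4% | 40/80 = 50.0% | 40/70 = 57.1% | 40/100 = 40% |
| 10 | 20% | 40/100 = 40.0% | 38/90 = 42.2% | 36/80 = 45.0% | 34/70 = 48.6% | 34/100 = 34% |
| 5 | 0% | 40/100 = 40.0% | 40/95 = 42.1% | 40/90 = 44.4% | 40/85 = 47.1% | 40/100 = 40% |
| 5 | 20% | 40/100 = 40.0% | 39/95 = 41.1% | 38/90 = 42.2% | 37/85 = 43.5% | 37/100 = 37% |

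Exact (Clopper-Pearson) 95% limits, assumed because the SAP says only that binomial methods are used, are 44.7 to 68.9% for 40/70 and 30.3 to 50.3% for 40/100.

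Seizure-free rates behave the same way. With 20 of 100 seizure-free throughout and 10 others leaving per window, they are 20/100, 20/90, 20/80 and 20/70 = 20.0, 22.2, 25.0 and 28.6%.

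**3. Non-selective dropout.** If 10% of responders and of non-responders leave in each of windows 1 to 3, the planned rate stays at 40%. The all-ITT rate in window 4 is 40 × 0.9³ = 29.2%.

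**4. Boundary visits.** If all 10 leavers in each window stop exactly at the boundary visit and count as entering the next window, window 4 in the first row becomes 40/80 = 50.0%, which is 57.1 − 50.0 = 7.1 points lower. This is an upper limit.

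**5. The interval of dropout.** A subject who leaves without a seizure so far has an SSF of zero on available data. That subject falls in the complete-reduction category of item 3 ("Further the relative change from baseline will be categorized into"), which Section 7.6 tabulates, and is a responder, but is not seizure-free. To size the chance element, let 5 to 10% of those entering leave uniformly over days 1 to 91 with an unchanged Poisson seizure rate. The mean chance of appearing to be a responder is 0.0793 at baseline SSF 8. Multiplied by 5 and by 10 per 100 entering, that adds 0.4 to 0.8 points. At SSF 4 the mean is 0.1495 (0.7 to 1.5 points). At SSF 8 with all leaving in days 1 to 30 it is 0.203 (1.0 to 2.0 points).

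**The case against.** Several parts of the case for leaving the text alone are sound.

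- **A reader might infer that the whole dropout rule is idle in later windows.** It is not. Anyone who leaves during window 2, 3 or 4 is a failure in that window, and anyone who leaves before Visit 7 is a failure overall. Only the carry-forward words do nothing to the window percentages.
- **A reader might infer that items 4 and 5 contradict each other.** They do not. Freedom from seizures needs the whole interval observed, whereas a 28-day rate can be computed from part of it, and the SAP specifies both rules. The difference is confined to the interval of dropout and the overall period. It is unexplained and its chance component is small.
- **The 57.1% figure is an extreme.** It needs 30% attrition with no responder ever leaving. If 20% of leavers are responders it is 48.6%, or 43.5% with 5 leaving per window.
- **The SAP already exposes attrition.** Completion (5.2.2 item 7) uses the ITT population with a confidence interval. Retention (item 8) counts withdrawal of consent, loss to follow-up, physician decision and other reasons as lack of efficacy. A reader is not left with the window rates alone, although neither analysis corrects them.
- **An all-ITT rate is not the right answer either.** It falls with dropout even when effect is maintained in those who stay, as step 3 shows.

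This is also a single-arm, open-label extension with a safety primary objective and no statistical sample size. All of this lowers the severity. None of it gives the carry-forward words an effect on a later window, or prevents selective dropout from raising the window 2 to 4 rates.

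**Conclusion.** The point holds in a limited form and is minor. If entering a window means still being in the study when it opens, carrying the failure forward changes later-window percentages by 0.0 points, and the seizure-free and responder rates in windows 2 to 4 can rise with no subject improving. Under the assumed scenarios, the window 4 responder rate exceeds the all-ITT rate by 6.5 points (43.5 against 37%) to 17.1 points (57.1 against 40%). Part of that gap is the all-ITT rate's own fall with dropout: where 20% of leavers respond, the rise from window 1 is 3.5 to 8.6 points. The true size depends on how many leave and who they are, which the documents do not say.

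If the sponsor meant every ITT subject to enter every window, the carry-forward words would work; the text does not read that way. The primary safety objective is untouched.

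**What to change.** Keep the planned tables and the available-data rule in Section 6.2, and make these additions.

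- In Section 7.6, add supplementary seizure-free and responder rates with 95% confidence intervals for windows 2 to 4. Use all ITT subjects as the denominator and count anyone who discontinued in or before the window as a failure.
- For responders, also give window 1 and overall under this rule. Seizure-free needs no extra rows there, because every ITT subject enters those two periods and the planned rule already counts dropouts as failures.
- Show the number entering each window.
- In 5.2.2 items 4 and 5, state whether a subject who discontinues at a boundary visit enters the next window.
- In item 4, refer to Section 6.2, and say that the failure rule applies only to the supplementary responder table, which need not match the item 3 categories.

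The cost is some SAP wording and one extra set of tables, with no new data. The supplementary rates fall with dropout even where effect is maintained in those who stay, so they must be read beside the planned tables.

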**6. Seizure frequency by seizure type**

SSF will be calculated by seizure type using the same methods described in #2 of this section.

**7. Completion rates**

Study completion is defined as the proportion of subjects from the ITT population who completed the entire 1-Year Open-Label Period (Visit 1 to Visit 7).

**8. Treatment retention time (time to withdrawal due to lack of efficacy or adverse events).**

If a subject's reason for withdrawal from 1-Year Open-Label Period included: withdrawal of consent, lost to follow-up, physician decision or other, then it will be assumed the subject terminated due to lack of efficacy. For subjects that discontinue due to adverse event or lack of efficacy, the treatment retention time during the 1-Year Open-Label Period will be calculated as the date of last known dose during the 1-Year Open-Label Period minus the date of the first dose of eslicarbazepine acetate monotherapy in protocol 093-045 or 093-046 (Visit 6/Week 8), plus 1. The time may include taking eslicarbazepine acetate concomitantly with other AEDs.

**5.2.3. Post-1-Year Open-Label Period Endpoints**

**1. Patient Global Impression**

PGI measures the effect of study drug by assessing patient overall impression on a 5-point scale from 0 (best score) to 4 (worst score), including:

- Very much improved
- Improved
- No change
- Worse

- Very much worse

PGI will be summarized from Visit 8 every three months during the Post-1-Year Open-Label Period until the End of Study or Early Termination Visit.

## **2 Completion rates**

Completion rates for Post- 1-Year Open-Label Period will be defined as the proportion of subjects from the ITT population who had the reason for withdrawal from the Post- 1 Year Open-Label Period either “Sponsor terminates clinical study” or “Study drug became available in subject’s locale” from the end of study page in the CRF.

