## 3. Study design

### 3.1. General Description

This study is a long-term, multicenter, open-label, safety extension study in male and female subjects (aged 16 to 70 years, inclusive) with partial onset seizures who have just completed, discontinued, or exited the 18-week treatment phase of Protocols 093-045 or 093-046. The initial study duration is 1-Year Open-Label Period with the option of continuing study drug treatment Post-1-Year Open-Label Period until a subject discontinues study, the study drug becomes clinically available in the subject's locale, or the sponsor terminates the study drug clinical development program.

This study will evaluate the safety and maintenance of effect of long-term eslicarbazepine acetate treatment at flexible doses in the range of 800 mg to 2400 mg once-a-day (QD) over a 1-Year Open-Label Period and a Post-1-Year Open-Label Period.

[figure not shown]

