## **7. Statistical Analysis**

### **7.1 Analysis Populations**

The intent-to-treat (ITT) population will consist of all subjects who have taken any open-label study medication. The ITT population will be used for all safety and all efficacy analyses.

The per-protocol (PP) population will consist of all subjects in the ITT population who did not have any important protocol deviations. The per-protocol population will be used in an additional analysis of the efficacy endpoints and subject demographics and baseline characteristics.

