### **7.2 Disposition of Subjects**

The number and percentage of subjects who entered 1-Year Open-Label Period, who completed the 1-Year Open-Label Period, who discontinued during 1-year Open-Label Period (including reasons for discontinuations), who completed 1-Year Open-Label period but did not enter the Post-1-Year Open-Label Period, entered Post-1-Year Open-Label Period, and discontinued early (including reasons for discontinuations) for Post-1-Year Open-Label Period, and who completed Post-1-Year Open-Label Period will be summarized. The number and percentage of subjects who were in actual monotherapy used subgroup and PP population will be also summarized respectively.

Subject disposition will be summarized for the ITT population.

Listing of subject disposition will be provided.

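### The Post-1-Year completion rate is divided by the whole ITT population, so it reports cumulative completion from open-label start under a Post-1-Year label

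*SAP*

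**What the plan says.** SAP 5.2.3 item 2 defines the Post-1-Year completion rate as "the proportion of subjects from the ITT population who had the reason for withdrawal from the Post- 1 Year Open-Label Period" recorded as either sponsor termination or local availability of the drug. SAP 7.6 (Completion rate) plans the number, the proportion and a binomial 95% confidence interval for each period, and names no other denominator.

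SAP 7.1 fixes the population: "The intent-to-treat (ITT) population will consist of all subjects who have taken any open-label study medication". It also repeats the efficacy endpoints in the per-protocol population, which is a subset of ITT.

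Not every ITT subject reaches the second period. SAP 3.1 describes an initial year "with the option of continuing study drug treatment Post-1-Year Open-Label Period". SAP 7.2 gives a disposition line to those who discontinue in Year 1 and another to those "who completed 1-Year Open-Label period but did not enter the Post-1-Year Open-Label Period".

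The Year-1 counterpart, SAP 5.2.2 item 7, is worded in the same way: "Study completion is defined as the proportion of subjects from the ITT population who completed the entire 1-Year Open-Label Period".

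**The concern.** The numerator can contain only subjects who were in the Post-1-Year Period, because only they can have a reason for withdrawing from it. The denominator contains everyone treated. Year-1 discontinuers, and Year-1 completers who chose not to go on, are therefore counted as failing to complete a period they never began.

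For Year 1 the ITT denominator does what the label says, since every treated subject starts that year. The same phrase does not carry over to a period that only some of them start.

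Maintenance of effect over the Post-1-Year Period is part of a secondary objective (SAP 2.2), and completion is one of four endpoints listed for that period. A reader who sees a Post-1-Year completion rate will take it as retention among those who were in the period. The planned figure also absorbs Year-1 attrition and elective non-entry, and so will be lower than that, possibly by a wide margin.

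**Working it through.** The documents state no completion rate and no entry fraction, so there is no plan figure to reproduce. The check is an identity followed by an illustration.

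**Notation.** N = ITT subjects; E = ITT subjects who entered the Post-1-Year Period (a count planned in SAP 7.2); X = subjects with one of the two completion reasons; f = E/N; r = X/E.

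**Identity.** All X come from E, so the planned rate is X/N = (E/N) × (X/E) = f × r. It follows that:

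- the shortfall relative to the entrant rate is (r − f r)/r = 1 − f, whatever r is;
- the absolute gap is r(1 − f);
- since r ≤ 1, the point estimate cannot exceed f, even if every entrant completes. This cap applies to the point estimate, not to the upper confidence limit.

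The planned interval is built from X successes in N subjects, so it too is an interval for f × r.

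**Illustration.** Assumptions: f = 0.9, 0.7 or 0.5; r about 0.60; N = 348, the enrolment figure in protocol Amendment 3. The actual ITT size is not given, and apart from rounding to whole subjects the percentages do not depend on N.

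| f | E | X | Among entrants, X/E | As planned, X/N | Gap (points) |
|---|---|---|---|---|---|
| 0.9 | 313 | 188 | 60.1% | 54.0% | about 6 |
| 0.7 | 244 | 146 | 59.8% | 42.0% | about 18 |
| 0.5 | 174 | 104 | 59.8% | 29.9% | about 30 |

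**Sensitivity to r.** With r between 0.4 and 0.8 (assumed), the gap r(1 − f) is:

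- f = 0.9: 0.4 × 0.1 to 0.8 × 0.1, or 4 to 8 points;
- f = 0.7: 0.4 × 0.3 to 0.8 × 0.3, or 12 to 24 points;
- f = 0.5: 0.4 × 0.5 to 0.8 × 0.5, or 20 to 40 points.

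At f = 1 the two rates coincide.

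**Does another section supply the restriction?** SAP 4.2 revises this endpoint from by-visit to whole-period without mentioning entrants. The opening of SAP 7.6 assigns ITT to all efficacy analyses. Neither section narrows the denominator.

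**The case against.** The best defence is that the rate is cumulative by design. Items 3 and 4 of SAP 5.2.3, time on monotherapy and retention time, also carry a Post-1-Year label while counting from the first monotherapy dose in the parent studies. A completion rate from open-label start fits that pattern. It shows what share of treated subjects stayed to the end of the programme, without conditioning on those who chose to continue. This stands: the full-ITT figure is a valid quantity. What does not stand is its label, because nothing in the definition tells the reader that it is cumulative.

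A second defence is that ITT here names only the source population. The text offers no other denominator, and the identical Year-1 phrase does mean full ITT. A programmer following the definition would divide by all treated subjects.

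A third is that SAP 7.2 already tabulates entrants and Post-1-Year completers. That also stands, and it limits the harm, although the planned interval would still be for the cumulative quantity.

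Three stronger readings are tempting, and the documents do not support them.

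- *Post-1-Year adverse-event and vital-sign percentages are diluted too.* SAP 7.1 says "The ITT population will be used for all safety and all efficacy analyses", but SAP 7.7.1 and 7.7.4 state no denominator for the period-specific columns. That is missing detail, not a stated error. The restricted denominator for laboratory shifts in SAP 7.7.2 does not settle it either, because those summaries cover scheduled visits only up to Visit 7.
- *The plan breaks its own convention for completion.* The responder rate is "divided by the total number of subjects in the ITT population entering the period of interest", and for seizure freedom "for each interval the percent will be based out of the number of subjects in the ITT population entering each interval of interest". Both are Year-1 seizure endpoints. The seizure-free rule also carries discontinuers forward as failures into later intervals. They show that the SAP can write an entrant denominator when it wants one; they are an analogy and set no rule for completion.
- *The planned interval fails to cover the entrant rate.* The two rates share the same completers and estimate different quantities, so asking whether one interval contains the other rate tests nothing, least of all with f, r and N all assumed.

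**Conclusion.** The point holds as a mismatch between definition and label. As written, the Post-1-Year completion rate and its interval estimate f times the completion rate among entrants. This follows from the definitions alone and needs no assumption. The size does need one: f is not in the documents, and for assumed values of 0.9, 0.7 and 0.5 the point estimate is 10%, 30% and 50% lower, in relative terms, than the rate among entrants.

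The definition should be corrected, because following it literally yields a misleading figure rather than merely leaving a detail open. The consequence is modest: the summary is descriptive, no test or decision rule depends on it, and the entrant rate can be recovered from the disposition table. The conclusion does not extend to the safety summaries, and it does not make the cumulative rate invalid in itself.

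**What to change.** In SAP 5.2.3 item 2 and SAP 7.6 (Completion rate), make the denominator for the Post-1-Year rate and its 95% confidence interval the ITT subjects who entered the Post-1-Year Period, as counted under SAP 7.2. Apply the same restriction to the per-protocol repeat of this endpoint under SAP 7.1, that is, per-protocol subjects who entered. Leave the Year-1 completion rate on full ITT.

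If the sponsor prefers to keep the full-ITT figure, label it as cumulative completion from open-label start and present it beside the entrant-based rate, each with its own interval.

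The cost is a denominator phrase in each of the two sections and a matching line for the per-protocol analysis. The ITT entrant count is already planned, and the per-protocol count applies the same entry status to a subset, so no new data are needed. The reported Post-1-Year rate will be higher than under the current definition unless every ITT subject enters, and its interval will rest on fewer subjects.
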